Potential subjects will be made aware of the study by a member of their clinical team and agree to be approached by the study team. The study team's clinical patients and individuals who have previously agreed to be contacted for future research will be approached for study participation. Study recruitment and enrollment will take place privately via telephone or through a HIPAA compliant video call system. Potential participants will be provided information about the study and will review the consent form with a study team member.

Screening:

CF and NCFB screening: HIPAA form 4 waiver has been requested in order to screen participants with CF and NCFB who are current patients at Johns Hopkins. Individuals with CF and NCFB will be screened using an EPIC chart review to assess past medical history. After a participant has been deemed eligible, he or she will be contacted by a member of the study team

via phone to confirm details of study eligibility and assess interest in study participation. Following screening, if individuals are eligible and are interested in study participation, they will be provided with a copy of the study consent form for review. If individuals with CF and NCFB decline study participation, then their reason for not participating will be recorded for future feasibility analysis regarding BCG vaccination trials in these patient populations. Information regarding which individuals have declined study participation will be retained to ensure that individuals are not contacted more than once.

Healthy volunteer participants will be screened according to the CIR protocol (JH200).

- Pre-Screening Evaluation: The purpose of the pre-screening evaluation is to determine subjects' basic eligibility to participate in the screening study. This evaluation may be completed by phone or in-person. When we contact or are contacted by an individual who has expressed an interest in participating in a research study, the pre-screening evaluation is performed using IRB-approved tools. Following an IRB-approved screening script, the individual is provided with a general overview of the screening process and he/she is informed of the types of trials conducted at the CIR. We then request the individual's permission to administer an IRB-approved pre-screening questionnaire in order to determine basic eligibility.

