- Screening Visits: Adult subjects who are eligible for screening and express interest in participating in a study are scheduled for a screening visit. All potential screening procedures are described in the JH200 research plan but not all procedures will be performed on every subject. Specific screening procedures vary to minimize unnecessary procedures with considerations for subject safety and comfort, logistics as well as the current recruitment needs of the CIR. The screening study may require one or more visits of approximately 2-4 hours. Screening procedures will be performed at JHSPH facilities. Screening visit(s) will include HIV testing using enzyme-linked immunosorbent assay (ELISA), rapid antibody test and/or confirmatory test, if necessary. Healthy volunteers will also be asked to sign a Medical Release Form during the screening visit. In the event that an adverse event occurs during the course of the study, this Medical Release Form will be used to obtain relevant medical records to allow for appropriate adverse event tracking.
- Compensation for screening visits: Individuals will be paid \$80 for completion of a screening visit if they are found to be eligible and enrolled in the study.

Informed Consent:

Investigators, research coordinators, and other study team members will be responsible for approaching potential research participants to seek informed consent. Informed consent will occur either in person or remotely via DocuSign (details below). Participants will be given adequate time to consider the research study and ask questions prior to signing the consent form.

Healthy volunteer participants who are deemed eligible for this study during in-person screening visits may then complete the informed consent process immediately after the screening visit.

For remote consent we intend to use DocuSign, the Institution's approved and 21 CFR Part 11compliant software, to obtain a secure electronic signature. Once the IRB approves our consent form(s), we will use the IRB-approved consent form(s) as the base for the DocuSign template. The IRB-approved document will not be altered other than to overlay locations where signatures, initials, dates or other DocuSign fields will be added to create the study-specific DocuSign template.

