We will send the consent to the participant via DocuSign, providing a participant-specific code in advance of sending the document via DocuSign, that will be required when the participant accesses and signs the consent. The consent discussion may take place via phone or video conference (e.g. Zoom). Participants will be given adequate time to consider the research study and ask questions prior to signing the consent form. When ready to sign, the participant will enter their code, verifying that the person signing the consent is the person that we spoke with previously, and sign the consent within the DocuSign system. Once the participant has electronically signed, the study team member obtaining informed consent will be notified that the electronic form is ready for his or her signature. Once signing is completed by all parties, both the study team and the participant can download the signed consent as a PDF. The study team will also have access to the audit log and the Certificate of Completion. The study team will load the signed consent into Epic.

After the Informed Consent process is completed, the study team member will document the informed consent process and file the IRB consent document to the research record.

Procedures prior to in-person research activities during COVID-19:

Individuals will be screened for change in baseline respiratory or systemic symptoms potentially attributable to COVID-19 or recent COVID-19 exposures on both the day before (via phone) and the day of any in-person study activities. If we are unable to reach a participant via phone for COVID screening purposes the day before an in person study visit, the research staff will administer the baseline respiratory or systemic screening questions immediately upon arrival at the study visit. The study visit may be canceled and rescheduled if an individual screens positive.

Study visit 1 (day 1):

Medical History:

Inclusion and exclusion criteria will be reviewed. A detailed medical history will be obtained to record relevant comorbidities and concomitant medications (See **Appendix B - Schedule of study surveys/standardized instruments** and **Supplemental Study Documents – Medical history forms**). Vital signs (temperature, blood pressure, heart rate, respiratory rate and oxygen saturation), including height and weight will be recorded.

Patient reported outcome measures:

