e. Justification of why participants will not receive routine care or will have current therapy stopped.

N/A. All CF and NCFB participants will continue to receive routine standard care for bronchiectasis without any interruptions.

f. Justification for inclusion of a placebo or non-treatment group.

All participants will receive the intradermal BCG vaccination. There is no placebo or nontreatment group in this study. Following the results of this study, a larger, blinded, placebocontrolled trial may be designed. g. Definition of treatment failure or participant removal criteria.

The goal of this study is not to achieve efficacy in prevention of infections, but rather to assess biomarkers of immune protection that are altered by BCG vaccination of vulnerable populations. Study samples will not be analyzed in real time.

Given these factors, we do not have specific criteria for participant removal. If there are unforeseen circumstances during which a participant will not be able to present for study visits 2 and 3 (research phlebotomy visits), these will be evaluated on a case by case basis by the PI.

h. Description of what happens to participants receiving therapy when study ends or if a participant's participation in the study ends prematurely.

This is a single vaccine design and there is no further booster vaccine planned. Participants will continue to receive standard of care for their medical conditions during and after study completion.

5. Inclusion/Exclusion Criteria

• Inclusion criteria (CF/NCFB arms):

- Confirmed diagnosis of either CF or NCFB
- Adult male and non pregnant females ages 18-65 (inclusive)
- \circ FEV1 \geq 40%
- Willingness to participate in the study after all aspects of the protocol have been explained and written informed consent obtained.
- o Available for the study duration, including all planned follow-up visits

• Inclusion criteria (healthy controls):

- Adult male and non pregnant females ages 18-65 (inclusive)
- Negative HIV enzyme-linked immunosorbent assay (ELISA), rapid antibody test and/or confirmatory test, if necessary, at screening
- Willingness to participate in the study after all aspects of the protocol have been explained and written informed obtained
- Available for the study duration, including all planned follow-up visits

• Exclusion criteria (all arms):

- Current or prior history of active or latent TB (per report, not formally tested) or NTM infection
- Prior BCG vaccination

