- Previous vaccine in the past 4 weeks
- History of severe anaphylaxis to any vaccine or vaccine components
- History of organ/bone marrow transplantation or other immunosuppressing condition, including HIV
- Immunosuppressing drugs (including oral corticosteroids equivalent to >10mg of prednisone for 5 days) in the 30 days prior to study enrollment
- o Cirrhosis or portal hypertension
- Pregnant or breastfeeding

- Receipt of another investigational product in the last 28 days or planned receipt during this study
- Has any other condition that, in the opinion of the principal investigator, would preclude informed consent, make study participation unsafe, complicate interpretation of study outcome data, or otherwise interfere with achieving study objectives

6. Drugs/ Substances/ Devices

a. The rationale for choosing the drug and dose or for choosing the device to be used.

The BCG vaccine is given intradermally to infants and children worldwide to protect against disseminated TB in most countries except the US and Canada. Its dosing for intradermal vaccination and safety profile is well established.

We have specifically chosen the BGC vaccine to test its effects on NTM because the BCG vaccine has been shown to provide some protection against diseases other than TB by boosting the immune system through trained immunity. Furthermore, based on a recent study by Abate et al there is evidence that the BCG increases protective immunity against NTM in healthy subjects¹⁶.

Due to a current global shortage of BCG VACCINE TICE®, we have received approval from the FDA to use TICE® BCG labeled for intravesical use in this study. These products are identical in formulation, but are labeled differently to indicate different routes of administration.

For this study, the selected dose of BCG TICE® is 0.1mL (~1x10⁶ CFU), which is lower than the package insert dose of (0.2-0.3 mL of 2-3 x10⁷ CFU). The lower dose was chosen to be consistent with the BCG dose used in a recent study by Abate et al. that showed the BCG (TICE® strain) induced blood-based markers of protection against NTM in healthy controls¹⁶.

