Following BCG vaccination, it is expected that nearly all individuals will exhibit a positive tuberculin skin test (also referred to as a purified protein derivative test or PPD) for a period of approximately five to seven years. Thus, latent TB testing via PPD method may be confounded by BCG vaccination. However, latent TB status can still be accurately determined by diagnostics blood tests (ex: QuantiFERON-TB Gold and ELISPOT TB).

Common adverse events from intradermal BCG vaccination include pain at injection site, a local skin reaction at the site of vaccination, which may ulcerate and scar, cause regional suppurative lymphadenitis, and osteitis, a rare complication (approx. complication rate

0.39/1,000,000). The most serious complication of BCG vaccination is disseminated BCG infection. The most frequent disseminated infection is BCG osteomyelitis (0.01 to 43 cases per 1,000,000 doses). Fatal disseminated BCG infection has occurred at a rate of 0.06-1.56 cases/1,000,000 doses. These primarily have occurred in immunocompromised hosts who are excluded from participating in this study.

There are rare case reports that vaccination against other viral infections, including SARS-Co-V2 and influenza, can cause transient erythema at the site of previous BCG vaccination, with no longterm clinical consequences.

Rarely, BCG vaccination can lead to transient vaccine-induced lymphadenopathy, which may present diagnostic dilemma for women undergoing screening mammography for breast cancer.

Common adverse events from routine blood draws include mild pain at blood draw site, minor bleeding and/or bruising.

b. Steps taken to minimize the risks.

Experienced nursing and research staff from the JH CIR will perform the intradermal vaccinations and study blood draws.

To minimize concerns, we are excluding individuals with immunosuppression, children, elderly, and pregnant/breastfeeding participants.

To minimize confounding results on mammography, female participants will be advised to delay screening mammography performed for a minimum of 3 months following BCG vaccination.

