Appendix A: Schedule of sample collection

Study visit	Sample collection		
Screening visit (healthy volunteers	HIV ELISA, rapid antibody test and/or confirmatory test, if		
only)	necessary		
Visit 1	Urine pregnancy test		
	Blood draw (pre-BCG vaccination). Approximately 75cc		
	(total) of blood collected in: SST, lithium-heparin tubes,		
	PAXgene RNA, EDTA		
Visit 2 (Day 30 +/- 5)	Approximately 75cc (total) of blood: collected in: SST,		
	lithium-heparin tubes, PAXgene RNA, EDTA		
Visit 3 (Day 90 +/- 14)	Approximately 75cc (total) of blood: collected in: SST,		
	lithium-heparin tubes, PAXgene RNA, EDTA		

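### HIV is an exclusion in all three arms, but the study tests for it only in healthy controls, so an undiagnosed case in the CF or NCFB arm would pass screening and receive live BCG

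*Combined protocol and SAP*

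**What the plan says.** The exclusion list in section 5, which applies to all arms, includes "History of organ/bone marrow transplantation or other immunosuppressing condition, including HIV". It is worded as a history and names no test.

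For healthy controls, section 5 adds an inclusion criterion: "Negative HIV enzyme-linked immunosorbent assay (ELISA), rapid antibody test and/or confirmatory test, if necessary, at screening". Section 4a (Screening) carries this out at the controls' screening visit: "Screening visit(s) will include HIV testing using enzyme-linked immunosorbent assay (ELISA), rapid antibody test and/or confirmatory test, if necessary". In Appendix A the only row with an HIV test is the one labelled "Screening visit (healthy volunteers" (the label runs on to restrict the row to that group). No HIV sample is listed at visits 1 to 3.

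For the patient arms, section 4a says "Individuals with CF and NCFB will be screened using an EPIC chart review to assess past medical history". Those who appear eligible are then contacted "via phone to confirm details of study eligibility and assess interest in study participation". At visit 1, before vaccination, "Inclusion and exclusion criteria will be reviewed. A detailed medical history will be obtained to record relevant comorbidities and concomitant medications". The CF/NCFB inclusion list has no HIV criterion.

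On fatal disseminated BCG infection, section 8a says "These primarily have occurred in immunocompromised hosts who are excluded from participating in this study". Section 8b also lists the exclusion of people with immunosuppression among the steps that reduce risk.

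**The concern.** Section 3 describes BCG as a live attenuated vaccine, and the risk section leans on the exclusion of immunocompromised hosts. For HIV, that exclusion is backed by a laboratory result in one arm and by history in the other two. A history check finds only what has already been diagnosed. Someone never tested has no history of HIV and meets every criterion as written.

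The gap lies in the arms that section 4g describes as vulnerable, and the protocol does not explain why healthy people are tested and patients are not. At stake is the safety of any such participant, and whether the reassurance in section 8a holds to the same standard in every arm.

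**Working it through.** The plan states no figure on this point, so there is none to reproduce. The check has three parts.

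**1. What stands between a candidate and vaccination, by arm**

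| Step | Healthy controls | CF and NCFB |
|---|---|---|
| Screening (section 4a) | Screening visit with HIV test | Chart review, then phone confirmation |
| Entry criterion (section 5) | Negative HIV test, plus the all-arms history exclusion | All-arms history exclusion only |
| Visit 1 (section 4a) | Criteria review and medical history | Criteria review and medical history |
| Laboratory work at visit 1 (section 4a, Appendix A) | IGRAs and research assays, no HIV test | IGRAs and research assays, no HIV test |

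Section 4g adds that study samples are not analysed in real time, so the baseline draw would not reveal a case before the injection. Every check in the right-hand column depends on a diagnosis that already exists.

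**2. How many people, and how likely**

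Inputs: 60 CF, 60 NCFB and 60 controls (section 4a). The prevalence p of undiagnosed HIV among CF/NCFB candidates who pass screening is not in the documents, so a range is assumed.

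- Not tested by the study: 60 + 60 = 120 of 180, and 120/180 = 67%.
- Chance of at least one case among the 120: 1 − (1 − p)^120. Expected number: 120p.

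| Assumed p | Chance of at least one | Expected number |
|---|---|---|
| 0.05% | 1 − 0.9995^120 = 5.8% | 0.06 |
| 0.1% | 1 − 0.999^120 = 11.3% | 0.12 |
| 0.3% | 1 − 0.997^120 = 30.3% | 0.36 |

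These are chances of vaccinating someone unknowingly, not chances of harm. The documents give no complication rate specific to HIV.

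**3. Does it reach the primary comparison?**

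Inputs: 10% attrition and a 40% difference in slopes taken as clinically meaningful (section 7c).

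- Evaluable per arm: 60 × 0.9 = 54.
- If 1, 2 or 3 of the 54 had no response at all, the arm's mean response would fall by 1/54 = 1.9%, 2/54 = 3.7% or 3/54 = 5.6%.
- To produce a 40% deficit alone would take 0.4 × 54 = 21.6, about 22 complete non-responders in one arm.

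Against expected numbers well below one across both patient arms, the effect on the comparison is negligible.

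**The case against.** The strongest reply is that the plan is internally consistent. The all-arms criterion asks about history, and chart review, a phone call and a medical history are how one checks history. Section 8a says that immunocompromised hosts are excluded, not that they have been cleared by a laboratory test. This stands: the point is a gap in safety screening, not a contradiction.

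A second reply is that patients and controls reach the study by different routes. The patients are under care at the institution and have charts that may already hold HIV results; controls come through the immunization research center, and no such chart review is described for them. That is a plausible reason for the difference, but the protocol does not state it and does not require a result to be in the chart. The medical history forms are in supplemental documents outside this review, so they may ask about HIV testing. A reader might infer that all 120 patients have unknown HIV status. The documents show only that the study does not test them.

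A third reply is that an HIV test does not rule out other immunosuppression. That also stands. The other conditions in the exclusion have no specified test in any arm, so one cannot say that controls are cleared of immunosuppression and patients are not. The difference between arms concerns HIV alone.

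Lastly, the investigator may exclude anyone for whom participation would be unsafe, and section 8b sets out monitoring after vaccination. The first can act only on what is known, and the second begins after the vaccine has been given.

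**Conclusion.** The point holds as a matter of safety and equal entry standards. HIV is excluded in all arms and tested for in one; nothing in the documents would identify an undiagnosed case in the other two before live BCG is given. The study does not test 120 of 180 participants. Under assumed undiagnosed prevalences of 0.05% to 0.3%, the chance of at least one unknowing vaccination runs from about 6% to about 30%. The range rests wholly on that assumption, and on counting all 120 as lacking a recent negative result in the chart; it shrinks to the extent that charts hold one.

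A reader might go further and infer that undetected HIV could make CF or NCFB patients look immune-deficient beside tested controls. The direction is right, but the size does not support it: one complete non-responder among 54 moves the arm mean by 1.9%, against a threshold of 40%. No claim is made about the between-group comparison.

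**What to change.** Reconcile sections 4a, 5 and 8 and Appendix A so that HIV-negative status is documented before vaccination in all three arms. For CF and NCFB this could be either a recent negative result in the chart, with the investigators defining how recent, or the test already used for controls. Section 5 would then carry the criterion for every arm, and Appendix A would show where the test falls for patients without a chart result. If the history-only route is kept, the protocol should give the reason and qualify the statement in section 8a.

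The cost is modest: at most 120 tests of a kind already run for controls, fewer where charts hold a result. Visit 1 already includes a draw of about 75cc and, for women of childbearing potential, a pregnancy test that must be negative for the participant to continue. Consent wording and result counselling would be needed. A reactive result that needs confirmation could mean rescheduling the vaccination.

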The vaccination site will be examined for each participant to ensure proper healing and evaluated for any signs of adverse reactions. A digital photograph of the vaccination site will be taken for each participant, without any identifying information included in the photograph, and will be uploaded into each participant's file that is a safely stored under Virtual SAFE Desktop.

Laboratory procedures for study samples:

Study visit 1: pre-vaccination blood sampling:

Baseline testing will include formal latent TB test with T-spot IGRA, and Ag85A IGRA. Specialized analysis will include cytokine, flow, and infection assays.

Study visit 2 and 3 blood sampling:

These subsequent blood draws will be analyzed first to confirm BCG uptake. This will be done by analyzing BCG Ag-specific (including Ag85A) cytokine release using multiplex ELISA & RT-PCR as well as BCG Ag-specific T cell activation using flow cytometry with intracellular cytokine staining (ICCS). Serum cytokines will also be measured.

Blood will also be analyzed to determine if BCG vaccination elicits NTM crossreactive immune responses in CF and NCFB by analyzing *Mycobacterium avium* (*Mav*) and *Mycobacterium abscessus* (*Mab*) Ag-specific cytokine release and T-cell activation using multiplex ELISA and RT-PCR as well as flow cytometry with ICCS.

We will then determine if BCG vaccination alters NTM killing activity in PBMCs from CF and NCFB. This will be done by infecting human monocyte-derived macrophages (MDM) with *Mav* and *Mab* followed by washing. Autologous T cells expanded with BCG for 7 d will then be added at a ratio of 10:1 and co-cultured for 72 hrs at which time cells will be detergent-lysed and *Mav* or *Mab* CFU counts determined by plating.

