c. Justification and safety information if non-FDA approved drugs without an IND will be administered.

See above. We have received an IND exemption from the FDA for the use of BCG in this study (see Supplemental study documents).

7. Study Statistics

- a. Primary outcome variable.
 - BCG Ag-specific cytokine release
- b. Secondary outcome variables.
 - NTM cross protectivity
 - Development of lung infections among the CF/NCFB arms during the 6-month period
 - Markers of trained immunity
- c. Statistical plan including sample size justification and interim data analysis.

Sample Size Calculations: The primary hypothesis tests are based upon enrollment of 60 individuals within each study arm while assuming a conservative attrition and dropout rate of 10% in each study group. Due to the pilot nature of this project, participants that drop out of the study will not be replaced. Power calculations were based upon testing a mean difference in slopes between groups assuming a within-person correlation of observations of 0.1 and have assumed that baseline response will not differ between groups; preliminary data for standard deviation of markers was obtained from Abate et al. We will have 80% power to detect changes in the mean difference in slopes ranging from approximately 11% (TNF α) to 65% (IL17) for markers of BCG-stimulated immune response, NTM-induced cytokine, and NTM killing activity between the CF and control groups and between NCFB and control groups at each time point at a significance level of 0.05. Given the heterogenous responses in individuals, we consider a mean difference in slopes of 40%, indicative of an immune response deficiency, between groups to be a clinically meaningful difference.

For detecting differences in TI, we will have 80% power to detect mean differences ranging from approximately 10-70% of TI at each time point between groups at a significance level of 0.05 assuming the same conditions as above, with the exception that the time variable will be the pre/post-stimulus condition. We will repeat these analyses for each time point. We have based power calculations using Cohen's f^2 (multiple correlation/1- multiple correlation) due to the lack of available data in these populations to estimate mean differences.

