Statistical Plan: Demographic and clinical characteristics of each study group will be described. Descriptive statistics, including proportions means and standard deviations and medians and interguartile ranges will be used to summarize BCG-stimulated immune response and NTMinduced cytokine and NTM killing activity at each time point (0, 30 days and 90 days) for each study group. Log-transformations of markers will be performed if distributional assumptions indicate. The primary statistical procedures will utilize linear mixed models to evaluate the mean difference in each marker from time 0 to 30 days and from time 0 to 90 days. The model takes the following form: $E[Y_{ij}] = b_0 + b_1 time_j + b_2 group_i + b_3 group * time + a'z_i + \alpha_i$ where Y_{ij} is the marker of interest for subject i at time j, group denotes the CF/NCFB/control status, time is a numeric visit number, z_i can include a vector of potential confounders and α is a subject-specific random effect to account for within-person correlations of the outcome while assuming the outcomes follow a Gaussian distribution. The parameter b₃ is the parameter of interest here as it quantifies the effect of CF/NCFB status on changing markers from baseline. Importantly, this model specifically allows us to account for baseline differences between groups, if they do exist. Secondary analyses will leverage the full longitudinal data collection of each of the three time points utilizing the previously described methods.

Interim Analysis: An interim safety assessment will be conducted once 30 CF, 30 NCFB, and 30 healthy controls have been enrolled and have completed the intradermal BCG vaccination and the 30-day blood draw.

d. Early stopping rules.

If there are two or more of the same Grade 3 adverse events (severe or medically significant but not immediately life threatening; hospitalization or prolongation of hospitalization indicated; disabling; limiting self-care or ADLs), or a single Grade 4 adverse events (life threatening consequences; urgent intervention indicated), the study will be halted until the Data Safety Monitoring Board (DSMB) can meet to discuss the appropriate actions that should be taken.

8. Risks

a. Medical risks, listing all procedures, their major and minor risks and expected frequency.

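### The primary outcome is a class of measurements with no cytokine, antigen, assay or visit designated, and its tests at 0.05 have no multiplicity rule: about a 16% false-positive chance per cytokine on the likelier reading, about 9% on narrower ones

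*Combined protocol and SAP*

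**What the plan says.** The primary objective (Section 2) is to compare BCG uptake in CF and NCFB with uptake in healthy controls. The primary outcome in Section 7a is one line: "BCG Ag-specific cytokine release".

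Section 4a, on blood sampling at visits 2 and 3, describes the measurement. "These subsequent blood draws will be analyzed first to confirm BCG uptake", by analysing "BCG Ag-specific (including Ag85A) cytokine release using multiplex ELISA & RT-PCR". The antigen set is open, there are two assays, and no cytokines are listed for this outcome.

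Section 7c (Sample Size Calculations) refers to primary hypothesis tests based on "enrollment of 60 individuals within each study arm while assuming a conservative attrition and dropout rate of 10% in each study group" and "assuming a within-person correlation of observations of 0.1". It claims 80% power for detectable differences in slope of about 11% (TNF-alpha) to 65% (IL17). That range covers BCG-stimulated, NTM-induced and NTM-killing markers together, "between the CF and control groups and between NCFB and control groups at each time point at a significance level of 0.05". A 40% difference is called clinically meaningful.

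Section 7c (Statistical Plan) uses mixed models to "evaluate the mean difference in each marker from time 0 to 30 days and from time 0 to 90 days", with a "subject-specific random effect to account for within-person correlations of the outcome". Neither section gives an order of testing, an adjustment, or a rule for what counts as a positive primary result.

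**The concern.** The primary result should be one answer per population to whether BCG uptake differs from controls. As written, it could be taken from any cytokine, antigen or assay and from either visit, and each contrast is judged at 0.05 on its own. The chance that at least one difference appears when neither group truly differs is then above 5% even for one cytokine.

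A false positive here would be a reported immune-response deficiency in CF or NCFB that does not exist, and Section 4d says favourable results could lead to a larger placebo-controlled trial.

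The power statement has a related gap. Because the detectable range pools outcomes and runs from well below to well above 40%, the reader cannot tell whether the primary variable is sensitive to the difference the plan calls meaningful.

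**Working it through.** **Inputs from Section 7c.** 60 per arm less 10% gives 60 × 0.9 = 54 evaluable per arm. Within-person correlation is 0.1, the model has a subject random effect, the level is 0.05, and there are two comparisons and two windows. Sidedness is not stated; two-sided is assumed.

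**The plan's own figure.** The 11% to 65% range cannot be reproduced, because no marker means or standard deviations are given. In standardised form, the difference detectable with 80% power is (1.960 + 0.842) × √(2/54) = 0.54 SD of the change score.

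**Correlation among the four tests, for one cytokine, antigen and assay.**
- Between windows: under a random intercept, each change has variance 2σ²(1 − ρ), and the two changes share the baseline, so their covariance is σ²(1 − ρ). The correlation is 0.5 whatever ρ is.
- Between comparisons: with equal arms and a shared control group, the correlation is 0.5.
- Across both: 0.5 × 0.5 = 0.25.

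**Chance of at least one p < 0.05 when all nulls are true.**

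| Reading | Chance |
|---|---|
| Four tests, correlations as above | 16% (16.1–16.2% by simulation) |
| Four tests, between-window correlation 0 | 17.3% |
| Four tests, between-window correlation 0.9 | 12.6% |
| Four independent tests, 1 − 0.95⁴ (upper reference) | 18.5% |
| One joint test over both groups per window, two windows | about 9% |
| Error counted per population, two windows | 9.1% |
| One variable and one visit, two comparisons, unadjusted | 9.1% |
| The same with Holm | 4.6% |

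A subject-level simulation with 54 per arm and ρ = 0.1 gave the same 16%. For scale, two cytokines tested in this way give 24% to 30%, for an assumed between-cytokine correlation of 0.8 to 0.

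**Power at a true 40% difference.** For a marker whose detectable difference is d, power is Φ(40/d × 2.802 − 1.960), if percentages scale linearly.
- d = 11: Φ(10.19 − 1.96) = Φ(8.23), essentially 100%.
- d = 65: Φ(1.724 − 1.960) = Φ(−0.236) = 41%.

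**Cost of Holm.** Its first step uses 0.025 (critical value 2.241).
- Power at a marker's own detectable difference: Φ(2.802 − 2.241) = 71%, or about 76% per comparison if both groups differ by that much.
- Power at a true 40% when d = 65: Φ(1.724 − 2.241) = 30%.

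**The case against.** **Four tests is a reading.** The wording about each time point and 0.05 comes from a power statement, not a decision rule. The model has a single interaction parameter of interest, a three-level group and time as a numeric visit number, so a joint test is not excluded. CF and NCFB are also distinct populations, and counting error separately for each is defensible. Either view gives about 9%. This stands, and the size has to be given as a range. Four tests remains likelier, because power is stated per comparison and per time point and the primary procedure names two windows.

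**This is a pilot.** Sections 4d and 7c say so, and Section 4g says the aim is to assess biomarkers rather than to achieve efficacy. That lowers the stakes. It does not remove the gap, because the plan itself states primary hypothesis tests, 80% power and a 0.05 level.

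**Missing a true deficiency may be the worse error.** Holm makes that somewhat easier. This is a real cost, and it is why intervals should be reported against 40%.

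**Stronger readings the documents do not support.**
- A reader might infer that nine cytokines are all primary, with a far higher error rate. The list in Section 4a belongs to trained immunity, a secondary outcome in Section 7b. TNF-alpha and IL17 appear in Section 7c only as the ends of a pooled power range.
- A reader might infer that the study cannot detect 40%. Only the upper end of the range suggests this, and nothing says that end applies to the primary variable.
- A reader might infer that the 40% figure already screens out chance findings. The plan never makes it a decision criterion.

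**Conclusion.** The point holds, with medium confidence. No primary cytokine, antigen, assay or visit is designated, and the stated testing has no multiplicity rule. For one cytokine, the false-positive chance is about 16% (13% to 17% for between-window correlations of 0.9 to 0) if there are four two-sided tests and CF and NCFB form one family. It is about 9% under a joint test per window or per-population counting. Both exceed the stated 0.05, and more cytokines, antigens or assays push them higher.

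Separately, the pooled power range leaves sensitivity to a 40% difference unknown, from near 100% at one end to about 41% at the other. The 41% assumes linear scaling. Section 7c allows log-transformation, and if the percentages are ratios on the log scale it would be about 28% (reductions) or 47% (increases). The sponsor should fix this, but it is not a fatal flaw in a pilot.

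**What to change.** Section 4g says samples are not analysed in real time. If none has yet been analysed:

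1. In Section 7a, name one primary cytokine, stimulating antigen, assay and visit, chosen because it best reflects BCG uptake.
2. In Section 7c, test CF against control and NCFB against control on that variable with Holm at two-sided 0.05, and write out the two model contrasts. Each comparison can succeed without the other, although a p-value between 0.025 and 0.05 counts only if the other is below 0.025. If full independence is wanted, use Bonferroni at 0.025 each.
3. Label the other visit and all other markers secondary or exploratory.
4. Replace the pooled 11% to 65% statement with the power at 40% for the named variable under this rule.
5. Report each difference with its 95% confidence interval, set against 40%.

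The change is wording in Sections 7a and 7c, with no added participants, visits or assays. The other markers lose primary status. Power at the named variable's own detectable difference falls from 80% to 71% (about 76% per comparison if both groups differ), so a true deficiency is somewhat easier to miss.
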